## **2 Study objectives and endpoints**

### **2.1 Primary objective(s)**

- To evaluate the efficacy of rivastigmine patch with 1-step titration on cognitive function measured as change from baseline to week 24 in the total score of MMSE in mild to moderate AD patients who failed to benefit from other ChEIs.

### **2.2 Secondary objective(s)**

- To evaluate the safety, tolerability of rivastigmine patch with 1-step titration for up to 24 weeks.
- To evaluate the efficacy of rivastigmine patch with 1-step titration measured as the MMSE score at week 8.
- To evaluate the efficacy of rivastigmine patch with 1-step titration measured as the NPI-10 score at week 8 and week 24.
- To evaluate the efficacy of rivastigmine patch with 1-step titration measured as QOL-AD score at week 24.
- To evaluate the efficacy of rivastigmine patch with 1-step titration measured as the J-CGIC score at week 4, week 8, week 16, and week 24
- To evaluate the efficacy of rivastigmine patch with 1-step titration measured as Modified Crichton Scale score week 4, week 8, week 16, and week 24.
- To evaluate the formulation usability of rivastigmine patch for up to 24 weeks as measured by the formulation usability questionnaire answered by caregiver.

## 2.4 Objectives and related endpoints

**Table 2-1 Objectives and related endpoints- Objectives**

| OBJECTIVE  | Endpoint Title, Description and Reporting Time Frame for analysis and Unit of Measure   | Stat Analysis Section       |
|--|---|-----------------------------|
| Primary   |   |                             |
| To evaluate the efficacy of rivastigmine patch with 1-step titration on cognitive function measured as change from baseline to week 24 in the total score of MMSE in mild to moderate AD patients who failed to benefit from other cholinesterase inhibitors (ChEIs) | Endpoint Title: Change from baseline to week 24 in the total score of MMSE
Time Frame : Up to week 24                              | Section 9.4 |
| Secondary   |   |                             |
| To evaluate the safety, tolerability of rivastigmine patch with 1-step titration for up to 24 weeks.   | Endpoint Title: Monitoring and recording of all adverse events (AEs) and serious adverse events (SAEs).
Time Frame: Up to week 24. | Section 9.5 |
| To evaluate the efficacy of rivastigmine patch with 1-step titration measured as the MMSE score at week 8.   | Endpoint Title: Change from baseline to Week 8 in MMSE total score.
Time Frame : Week 8  |                             |
| To evaluate the efficacy of rivastigmine patch with 1-step titration measured as the NPI-10 score at week 8 and week 24.   | Endpoint Title: Change in NPI-10 score from baseline to week 8 and week 24
Time Frame : Week 8 and Week 24                         |                             |
| To evaluate the efficacy of rivastigmine patch with 1-step titration measured as QOL-AD score at week 24.  | Endpoint Title: Change in QOL-AD score from baseline to week 24
Time Frame : Week 24   | Section 9.5 |
| To evaluate the efficacy of rivastigmine patch with 1-step titration measured as the J-CGIC score at week 4, week 8, week 16, and week 24.   | Endpoint Title: Change in J-CGIC score from baseline to week 4, 8, 16 and 24
Time Frame : Week 4, 8, 16, 24                        |                             |

| OBJECTIVE  | Endpoint Title, Description and Reporting Time Frame for analysis and Unit of Measure  | Stat Analysis Section |
|--|--|-----------------------|
| To evaluate the efficacy of rivastigmine patch with 1-step titration measured as Modified Crichton Scale score week 4, week 8, week 16, and week 24.         | Endpoint Title: Change in as Modified Crichton Scale score from baseline to week 4, 8, 16 and 24

Time Frame : Week 4, 8, 16, 24 |                       |
| To evaluate the formulation usability of rivastigmine patch for up to 24 weeks as measured by the formulation usability questionnaire answered by caregiver. | Endpoint Title: Formulation usability score up to week 24

Time Frame : Up to week 24  |                       |

### 3      Investigational plan

#### 3.1    Study design

This is a 24-week, multi-center, open-label, single-arm (1-step titration) study in patients with mild to moderate AD (MMSE 10-23) switched directly from cholinesterase inhibitors (donepezil, galantamine) for AD.

The study will have three phases

##### 1. Screening phase [2-4 weeks: week -4 (Day -28) to week -2 (Day -14 to Day -1)].

The Screening Visit (Visit 1) has to take place 2 – 4 weeks before the planned start of rivastigmine patch treatment. After signing the informed consent, all patients will undergo a preliminary evaluation (Screening Visit) to assess eligibility (Protocol [section 4.1](#)). Patients will continue their ChE inhibitors (donepezil or galantamine) during the Screening period, and patients are eligible to take their ChE inhibitors until the evening prior to start day of rivastigmine patch. For those patients who are eligible to enroll the study by the preliminary evaluation at Screening Visit, MMSE score during previous 6 months should be collected and recorded as much as possible. Their ChE inhibitors are discontinued on Baseline visit (Day 1). At the baseline visit (Visit 2), the patient will also undergo safety and efficacy assessments as per [Table 6-1](#), and eligibility will be confirmed. Day 1 will be the day on which treatment with rivastigmine patch will be started. Patients will be starting on treatment with rivastigmine patch on the same day of the baseline visit (Day 1). When the patients already took their ChE inhibitors at the baseline visit (Visit 2, Day -1), the

patients will start on treatment with rivastigmine patch the next day (Day 1) after the baseline visit.

[figure not shown]
## 2. Titration phase [8 weeks: week 1 (Day 1) to week 8 (Day 56)].

On the same day or next day (Day 1) following baseline visit, patients will begin treatment with a rivastigmine patch 9.0 mg/day and will be up-titrated after 4 weeks to reach the maintenance dose of 18 mg/day. Should tolerability problems occur, the investigators can decide to interrupt the treatment temporarily or to reduce the dose (see [Section 5.5.5](#)). The highest well-tolerated dose for each individual patient should be established within the titration period. The investigators also can use their clinical judgement to switch those patients to slower 3-step titration scheme in order to reach the maintenance dose of 18 mg/day or find the highest well-tolerated dose for each individual patient. Those patients will be allowed to stay in the study. During the titration period, visits will take place every 4 weeks.

## 3. Maintenance phase [16 weeks: week 9 (Day 57) to week 24 (Day 168)].

The patients will be maintained on the maintenance dose of rivastigmine patch 18 mg/day (or highest well-tolerated dose) during the remaining period of the study and will undergo safety and efficacy assessments as per protocol. If 18 mg/day is not achieved at maintenance period, it will be increased up to 18 mg/day if possible. Patients not tolerating the 18 mg/day will stay on their highest tolerated dose in the study and will undergo safety and efficacy assessment as per protocol.

**Figure 3-1 Study design**

## 3.2 Rationale for study design

The patient population will be described in more detail in the [Section 4](#) below.

This study is a Phase IV study (post marketing study) to evaluate the efficacy, safety and tolerability of rivastigmine patch in patients with mild to moderate AD switching directly from oral ChE inhibitors (donepezil and galantamine) to rivastigmine patch with 1 step titration. Since the purpose of this study is not to prove superiority/non-inferiority, double-blind, placebo or active-controlled study is not needed.

The patients who are eligible to this study are those who are lack/loss of efficacy or having difficulties in administrating with previous oral ChE inhibitors. Active or placebo controlled study is not appropriate from an ethical point for patients.

In previous reported switch study, direct switching from donepezil to rivastigmine patch, was safe and well-tolerated ([Sadowsky 2010](#)). Another switching study in Japan, a 24-week, open-label, multicenter study to evaluate the efficacy, safety and tolerability of rivastigmine patch with 3-step titration in patients with mild to moderate Alzheimer's disease demonstrated the safety and well-tolerability of direct switch to rivastigmine patch for AD patients who have difficulties being treated with ChE inhibitors (donepezil and galantamine). Therefore, no washout period from the previous treatment is recommended for the study.

### **3.3 Rationale for dose/regimen, route of administration and duration of treatment**

Rivastigmine patch is a marketed drug, therefore the dose, dose regimen and titration scheme are in accordance with product label.

An AD patient who is applicable to 1 step titration method (initial loading dose is a rivastigmine patch 9.0 mg/day and will be up-titrated after 4 weeks to reach the maintenance dose of 18 mg/day) defined in [Section 4.1](#) is subject to the enrollment of this study. In principle, 1 step titration method should be applied to all of patients as long as tolerated.

The treatment period of 24-weeks is as per AD evaluation guideline EU ([EMEA 2008](#)), and Japanese guideline research ([Homma 1998](#)). FDA guidelines ([Leber 1990](#)) specify that at least 3 months as treatment period is needed, and EU & Japanese guidelines mentioned that more than 6 months of treatment is required. Therefore, the treatment period for this study is also set for 24 weeks.

### **3.4 Rationale for choice of comparator**

No comparator will be included based on the rationale of study design.

### **3.5 Purpose and timing of interim analyses/design adaptations**

Not applicable.

### **3.6 Risks and benefits**

The risk to subjects in this trial will be minimized by compliance with the eligibility criteria and study procedures, close clinical monitoring.

Rivastigmine patch is approved in more than 90 countries around the world. Approximately 17,144 patients received rivastigmine treatment in Novartis-sponsored investigational clinical trials. It is estimated from marketing experience (post-authorization exposure) that the

cumulative patient exposure of oral formulation is approximately 5,194,565 patient-years, and 3,912,326 patient-years of treatment with the transdermal formulation. Tests done in this study at each visit are standard medical tests. The risks of taking blood may include fainting, pain and/or bruising at the site of needle puncture or finger sticks. The risk to subjects in this trial will be minimized by compliance with the inclusion/exclusion criteria and close clinical monitoring.

Japanese pivotal Phase IIb/III clinical study (CENA713D1301 study), a 24-week, double-blind, randomized, placebo control, in AD patients (MMSE 10-20) demonstrated that rivastigmine patch 18 mg/day was statistically significant over placebo on the ADAS-J cog at week 24 ([Nakamura. et al, 2011](#)), and showed that most frequent observed AEs were application site erythema, application site pruritus, and contact dermatitis which developed regardless of starting dose and titration.

Overall, the incidence rate of skin reactions in the Japanese population was higher compared to the observed incidence rate in other global studies.

CENA713D1403 in Japan, a 24-week, open-label, multicenter study to evaluate the efficacy, safety and tolerability of rivastigmine patch with 3-step titration in patients with mild to moderate AD switched from ChE inhibitors (donepezil, galantamine) showed the safety and well-tolerability of direct switch to rivastigmine patch for those who had difficulties being treated with ChE inhibitors (donepezil and galantamine).

CENA713D1303 study results showed the safety and tolerability of the 1-step titration method is comparable to the slower 3-step titration method in the Japanese mild to moderate AD population. The tolerability of the 1-step titration method was evaluated by comparing the proportion of patients with AEs leading to discontinuation with the 3-step titration method. The proportion of patients who discontinued the study drug treatment due to AEs was 15.0% (16/107) in the 1-step titration group and 18.5% (20/108) in the 3-step titration group. The observed difference between treatments of the proportion of discontinuation due to AEs were -3.6% (95% CI: -17.0, 9.6, Exact method). Since the point estimate of the observed difference falls within the pre-specified acceptance range (i.e. [-9.0%, 9.0%]), the study met its primary objective. The study showed similar efficacy in ADAS-J cog and MMSE score between the 1-step titration and the 3-step titration group at week 24. At week 8, the 1-step titration group showed a slightly greater improvement compared to the 3-step titration group in ADAS-J cog, potentially suggesting an earlier efficacy onset with the quicker titration.

In conclusion, it is clinically meaningful to assess a benefit of quicker titration method to reach the maintenance dose of 18 mg/day and to explore if switching therapy from oral ChE inhibitors to rivastigmine patch with 1 step titration could be a suitable treatment option.

## 4 Population

The study population will consist of a representative group of male and female Japanese patients (50-85 years of age) with probable AD Mini – Mental State Examination (MMSE 10-23), treated with donepezil or galantamine.

This is the multicenter study that will enroll a total of approximately 120 patients which will be switched to rivastigmine patch with 1-step titration in Japan. Since a 30% screening failure rate is expected, 170 patients have to be screened.

#### **4.1 Inclusion criteria**

Patients/subjects eligible for inclusion in this study must fulfill all of the following criteria:

1. Written informed consent of the patient and legal representative will be obtained before any assessment is performed (MUST be signed by the legal representative if a signed informed consent from patients is difficult, consent can only be obtained from the patients orally) at Screening.
2. Patients within the age of 50-85 years at Baseline.
3. Outpatient status at Baseline.
4. Males and females not of child-bearing potential.
  - Women are considered post-menopausal and not of child bearing potential if they have had 12 months of natural (spontaneous) amenorrhea with an appropriate clinical profile (e.g. age appropriate, history of vasomotor symptoms) or have had surgical bilateral oophorectomy (with/without hysterectomy) or tubal ligation at least six weeks previously.
5. A diagnosis of dementia of the Alzheimer's type according to the DSM-IV criteria.
6. A clinical diagnosis of probable AD according to National Institute of Neurological and Communicative Disorders and Stroke - Alzheimer's Disease and Related Disorders Association (NINCDS-ADRDA) criteria and meeting any of following criteria.
  - Brain scan (magnetic resonance imaging [MRI], or computed tomography [CT]) were met diagnosis criteria conducted within 3 years prior to baseline (Imaging within 1 year prior to baseline is preferable).
  - Positron emission tomography (PET) or single photon emission computed tomography (SPECT) was met diagnosis criteria conducted within 3 years prior to baseline visit; as long as in the past a brain scan (MRI or CT) was also met (Imaging within 1 year prior to baseline is preferable).
7. An MMSE score of  $\geq 10$  and  $\leq 23$  at screening and baseline.
8. Patients are currently on the oral monotherapy (donepezil, 5 mg), or galantamine (16-24 mg) for 4 weeks prior to baseline visit.
9. Patients who could not receive treatment benefits of previous oral ChEIs can be defined by meeting the following criteria, either 9-1, 9-2, or both.
  - 9-1. Patients who are not responding to the previous treatment can be defined if the patients meet at least one of these conditions at screening and baseline
    - Patients who declined  $\geq 2$  points of MMSE despite of treatment of other oral ChE inhibitors within initial 3-month and continued to show insufficient treatment effect until at baseline.
    - During 6 months prior to screening visit, patients who declined  $\geq 2$  points of MMSE with other oral ChE inhibitors and continued to show insufficient treatment effect until at baseline.

- Patients who show marked worsening of BPSD, or ADL (can be defined by 1 state progression of FAST) judged by a physician despite of treatment of other oral ChE inhibitors in initial 3-month or last 6-month with other oral ChE inhibitors
- 9-2. Patients having difficulties being treated orally with ChEIs (donepezil or galantamine) by physician's judgement. Difficulties are defined if the patients meet at least one of these conditions at screening and baseline:
  - Inadequate compliance with the ChE inhibitors at screening and baseline
  - Inadequate treatment (efficacious dose was not reached or inadequate compliance) with the ChE inhibitors because of AEs except gastrointestinal (GI) symptoms (nausea and vomiting) at screening and baseline
  - Patients with swallowing difficulties at screening and baseline

10. Sufficient education to be able to read, write, and communicate effectively during the premorbid state

11. Cooperative, willing to complete all aspects of the study, and capable of doing so, either alone or with the aid of a responsible caregiver

12. Residing with someone in the community throughout the study or, if living alone, in contact with the primary caregiver every day

13. A primary caregiver willing to accept responsibility for supervising the treatment, (e.g., application and removal of the patch daily at approximately the same time of the day) assessing the condition of the patient throughout the study, and for providing input to efficacy assessments in accordance with all protocol requirements. The caregiver was required to be able to directly assess the condition of the patient during the day and night 4 or more days a week.

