##### **9.4.2 Statistical model, hypothesis, and method of analysis**

The change from baseline in MMSE total score will be analyzed using a mixed model repeated measures (MMRM) model. The model will contain visit as a fixed effect, baseline MMSE score as a covariate and subject as a random effect. An unstructured covariance matrix will be used to model the within-subject error. The estimated mean change at Week 24 along with a two-sided 95% confidence interval and p-value will be presented. P-values will be used in descriptive manner.

Further, the MMSE total score and change from baseline will be summarized using standard descriptive statistics by visits.

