## **9.8 Sample size calculation**

The sample size is determined as precision-based for the change from baseline in MMSE score at week 24. Ninety-seven patients will ensure that the half-width of 95% confidence interval for the change from baseline in MMSE score at week 24 would be 0.6, assuming SD=3.0 which is estimated from 1301, 1303 and 1403 study. Assuming drop-outs, a total of 120 patients will be enrolled to achieve at least 97 evaluable subjects.

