2.1.1.3 Baseline definition

Baseline visit (typically Visit 2) is defined as the day on which patients discontinue their prior ChE inhibitors. The baseline visit (Visit 2) may or may not be the same as Day 1. .

- It will be same as Day 1 if the patients already stop their ChE inhibitors prior to Day 1 and starts treatment with revastigmine patch from Day 1.
- on the otherhand, baseline visit (Visit 2, Day -1) will be one day before the Day 1 start of study treatment if the patients already took their ChE inhibitors at Visit 2.

In general, all assessments taken prior to the start of study treatment at Visit 2 will be considered as the baseline assessment. However, if the baseline assessments for MMSE, vital signs and laboratory parameters at Visit 2 are missing, then the measurements taken at Visit 1 (if available, as per protocol assessment schedule Table 6-1) will be used as baseline.

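### Criterion 9-1 lets sites re-check the MMSE decline on the Visit 2 score that is also the primary baseline; where they do, regression to the mean inflates the Week 24 change

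*Protocol*

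**What the plan says.** Protocol 4.1, criterion 9-1: non-response to the previous inhibitor "can be defined if the patients meet at least one of these conditions at screening and baseline". There are three routes.

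- Item 1: an MMSE fall of at least 2 points on oral treatment "within initial 3-month and continued to show insufficient treatment effect until at baseline".
- Item 2: a fall of at least 2 points during the 6 months before screening, where the patient also "continued to show insufficient treatment effect until at baseline".
- Item 3: physician-judged worsening of behavioural symptoms or daily living. No MMSE fall is needed.

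Criterion 9-2 (compliance, non-gastrointestinal adverse events, swallowing) is an alternative entry that also needs no MMSE fall. SAP 2.2.1.1 restates 9-1 as conditions met at baseline and does not mention screening. Neither document defines insufficient treatment effect.

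Protocol Table 6-1 schedules both the MMSE and the eligibility check at Visits 1 and 2, and Protocol 3.1 has eligibility confirmed at Visit 2. Criterion 7 requires an MMSE of 10 to 23 at both visits.

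Under SAP 2.1.1.3 the Visit 2 assessment is the baseline, except that "if the baseline assessments for MMSE, vital signs and laboratory parameters at Visit 2 are missing, then the measurements taken at Visit 1" are used instead. The primary analysis pools all entry routes in the FAS, and Protocol 9.4.2 states: "The estimated mean change at Week 24 along with a two-sided 95% confidence interval and p-value will be presented". There is no comparator (Protocol 3.4).

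**The concern.** A score that helped a patient qualify because it was low tends to be higher at the next test, whatever the treatment. If the Visit 2 MMSE is used to decide whether the 2-point fall still stands, patients whose score rebounds by chance are screened out and those with a chance low score are enrolled. The same score is then the starting point of the primary change.

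The design has no control arm to show the same rise. The estimated mean change is the main result of the study, so an artefact in it would be read as benefit from the patch. It would also raise the responder rate added in SAP Section 4, where unchanged or improved counts as response. More patients would not help, because a larger sample narrows the interval around a biased value. Sites may also read the criterion differently, so the size of the problem could vary between sites.

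**Working it through.** **1. The plan's own figure.** Protocol 9.8: "Ninety-seven patients will ensure that the half-width of 95% confidence interval for the change from baseline in MMSE score at week 24 would be 0.6". The SD of the change is taken there as 3.0, from three earlier studies. n = (1.96 × 3.0 / 0.6)² = 96.04, rounded up to 97. At n = 97 the half-width is 1.96 × 3.0 / √97 = 0.597. The figure reproduces, and 0.6 is the yardstick used below.

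**2. What the text fixes.** The decline in item 1 falls in the first 3 months of earlier treatment. The decline in item 2 falls in a window that ends at screening. What must last to baseline is insufficient effect, with no measure attached. Two readings are therefore open: (a) the decline is settled by Visit 1; (b) it must still be present in the Visit 2 score.

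**3. Size under each reading.** Simulation, 1,000,000 candidates per cell, with no true change after baseline.

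- From the documents: SD of a change between two tests 3.0; range 10 to 23; decline of at least 2 points.
- Assumed: retest error SD (s) 1.0, 1.5 or 1.8; mean prior change (m) 0, −1 or −2; true score N(18, 3.5²); independent errors at each test.
- Model: true prior change ~ N(m, 9 − 2s²); integer scores; X0 = historical score, X1 = Visit 1, X2 = Visit 2, W = Week 24.
- Rule (a): X0 − X1 ≥ 2 and X1 in range. Rule (b): the same, and also X0 − X2 ≥ 2 and X2 in range.
- Artefact = mean of W − X2 among those selected.

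| s | m = 0 | m = −1 | m = −2 |
|---|---|---|---|
| 1.0, rule (b) | +0.23 | +0.17 | +0.13 |
| 1.5, rule (b) | +0.53 | +0.41 | +0.31 |
| 1.8, rule (b) | +0.82 | +0.64 | +0.48 |
| any s, rule (a) | about 0 | about 0 | about 0 |

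A repeat run agreed within 0.01 in every cell. Under rule (b) the responder rate is about 4 to 14 percentage points higher than under rule (a), again with no true change.

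**4. Dilution.** The table applies to patients who enter by MMSE decline. If the other routes carry no artefact, the overall artefact is share × cell. At a share of one half, the range is 0.5 × 0.13 = 0.07 to 0.5 × 0.82 = 0.41, and the middle cell gives 0.5 × 0.41 = 0.21. Reaching 0.6 overall would need a share of 0.6 / 0.82 = 73% or 0.6 / 0.64 = 94% in the two largest cells. It is out of reach in the other seven.

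**5. A second model.** Candidate mean 18 and SD 4.5; prior decline 0.5 to 2 (SD 1 to 2); error SD 1.0 to 2.12, where 2.12 = 3.0/√2 is the value if the whole SD of 3.0 were error; 10 to 23 required at both visits.

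- Rule (b), all patients entering by MMSE decline: +0.17 to +1.01.
- Decline judged at Visit 1 only, independent errors: −0.03 to +0.11.
- Decline judged at Visit 1 only, Visit 1 and Visit 2 errors correlated at 0.3 to 0.6: +0.06 to +0.86.
- The 10 to 23 range alone, at error SD 2.0: −0.12 to +0.23, depending on the candidate mean (15 to 22).
- Adjusting for baseline MMSE left the artefact unchanged in every scenario.

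**6. The Visit 1 fallback.** Under rule (a), the mean of W − X1 is +0.22 to +1.22, because Visit 1 is then the score that showed the decline.

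**The case against.** The strongest reply is that the text never makes the Visit 2 MMSE the test of the decline. Both declines are dated earlier, and deviation I09 in SAP 5.2 ties the historical MMSE date to screening. A reader might infer from the words about screening and baseline that the plan itself selects on the Visit 2 score. The documents do not support that; they only fail to exclude it. The conditional form stands, because a site that re-checks the fall at Visit 2 is following the wording.

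Item 1 can also rest on two historical scores that involve neither study visit, and the simulation does not model that case. Item 3 and criterion 9-2 need no MMSE fall, and no enrolment share per route is planned. Both points reduce the overall effect by an unknown amount.

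The SAP already plans the Week 8 and Week 24 MMSE change by entry route, including 9-1-3 only and 9-2 only. That is a useful check, but it is not presented as one.

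The study does not aim to prove superiority or non-inferiority, its p-values are descriptive, and there is no success threshold. This lowers the stakes but does not protect the point estimate.

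The Visit 1 fallback should rarely apply, because criterion 7 requires a baseline MMSE.

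**Conclusion.** The point holds in conditional form. Where sites re-apply the MMSE decline at Visit 2, the primary change in MMSE decliners carries an upward artefact of about +0.1 to +0.8 points, and about +0.4 at error SD 1.5 and mean prior decline 1. Where the decline is settled by screening and visit errors are independent, it is about 0. The retest error, the prior decline and the share per route are assumptions; the documents give none of them.

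Two stronger conclusions should not be drawn. A reader might infer that the artefact matches the planned half-width. It reaches 0.6 in only 2 of 9 cells of the first model, both at error SD 1.8, and only if nearly all or most patients enter by MMSE decline. A reader might also infer that the 10 to 23 range adds to the bias. Its upper and lower limits pull in opposite directions, and the net sign is not fixed.

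The wording should be changed because the bias is avoidable at little cost. The sample size needs no correction.

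**What to change.** 1. Protocol 4.1: state that the MMSE decline in items 1 and 2 of 9-1 is judged on pre-study and Visit 1 scores only, and that the Visit 2 MMSE is not used to confirm it. Define insufficient treatment effect until baseline accordingly. Align SAP 2.2.1.1. Leave criterion 7 as it is.
2. SAP 2.5.4: place the already planned Week 24 change for 9-1 MMSE decliners, 9-1-3-only and 9-2-only patients beside the primary result as a regression-to-the-mean check. Add a caveat that these groups also differ clinically.
3. SAP 2.1.1.3 or 2.5.4: show the primary result without any MMSE decliner whose baseline is the Visit 1 fallback.

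A table of the Visit 1 to Visit 2 change in enrolled patients would not serve as the check. In the first model it averages 0.00 when both visits use the same rule and the bias is present. It is +0.22 to +1.23 when only Visit 1 is used and the bias is absent.

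Cost: wording changes and a rearranged table, with no new visit or test. Some patients whose Visit 2 score rebounds will enter, and the result may look less favourable. If errors at Visits 1 and 2 are correlated, change 1 reduces the artefact but does not remove it. If enrolment is already advanced, changes 2 and 3 remain available.
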